### Timing of secondary outcomes

*Protective immunity:* Proportions with protective neutralising antibody (YF), i.e. neutralising antibody>1/5; protective IgG levels (TT), i.e. IgG>0.1 IU/ml; seroconversion rates (Ty21a) at four weeks post the corresponding immunisation (week 8).

*Response waning:* Primary outcome measures for all vaccines repeated at week 52 except for Td whose primary outcome responses are measured at week 52.

*Priming versus boosting:* HPV vaccine responses four weeks after the priming dose (week 8) and 24 weeks after the boosting dose (week 52).

Current malaria infection status and intensity at screening (week -8), weeks 0, 4, 8, 52.

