# Analysis population for the secondary outcomes

*Protective immunity:* Analysis population for YF, Ty21a and Td protective immunity will include all enrolled participants who receive the respective vaccine (YF-17D, Ty21a at week 4, Td vaccine at week 28) and have responses to the respective vaccines at 4 weeks post vaccination for YF-17D, Ty21a and 24 weeks post Td vaccination.

*Response waning:* Analysis population will include all enrolled participants who receive any of BCG, YF-17D, Ty21a, HPV and Td vaccines; have corresponding responses to any of these vaccines at weeks 8, 28 (for Td vaccine) and 52 post vaccination.

*Priming versus boosting:* Analysis population will include all enrolled participants who receive a priming dose of HPV vaccine at week 4 and a boosting dose at week 28 and have corresponding responses to the vaccine (at weeks 8 and 52).

Current malaria infection status and intensity: Analysis population will include all enrolled participants who have serum/plasma samples and corresponding results at any of these time points; baseline (week -8), on immunisation days (weeks 0, 4, 8 and 28), and on primary (weeks 8 and 52) and secondary endpoint days (week 52).

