# 4.2. Baseline characteristics

Participants will be described with respect to their baseline characteristics including age, sex, school, location of birth, prior vaccination status, malaria infection status both overall and separately for each arm.

Categorical variables will be summarised by numbers and percentages. Continuous variables will be summarised by mean, SD and range if data are normal or median, IQR and range if data are skewed. No statistical tests will be done to compare baseline characteristics between arms.

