### 5.1.2. Outcomes for secondary objective

- *Protective immunity:* Proportions with protective neutralising antibody (YF), i.e., >1/5; protective IgG levels (TT), i.e., >0.1 IU/mL; seroconversion rates (Ty21a).
- *Response waning:* Primary outcome measures for all vaccines repeated at week 52.
- Priming versus boosting: IgG specific for L1-proteins of HPV-16/18.
- Current malaria infection status and intensity: Infection status (infected and uninfected) and intensity (light, medium and heavy).

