# 5.2.2. Analysis of secondary objective outcome measures

*Protective immunity:* Proportions of participants in each category will be presented by trial arm and comparisons between trial arms will be made using chi square test.

*Response waning:* Area under the curve will used for analysis of response waning. Response measurements from weeks 8 and 52 will be used for this analysis.

*Priming versus boosting:* Mean HPV responses will be presented, and a paired t test will be used to compare HPV responses at weeks 8 and 52. In addition, a linear regression model including a time\*trial arm interaction term will be fitted to assess whether the intervention has a differential effect on the response to priming and than to boosting.

*Current malaria infection and intensity:* Proportions of participants with malaria infection will be presented at each timepoint by trial arm and comparisons between trial arms will be made using chi square test. At each timepoint, the means (SD) of malaria infection intensity will be presented by trial arm, and comparisons between trial arms will be made using unpaired t-tests. For both malaria infection status and intensity, Generalised Estimating Equations (GEE) will be used to estimate and compare malaria status and intensity changes between the trial arms.

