### Checking assumptions

For statistical analyses that require data to be normally distributed, the normality assumption of the data will be checked using graphical assessment of normality (Q-Q plot) and a Kolmogorov-Smirnov test for normality. If the data are found to be non-normal, medians (IQR) or geometric means (SD) will be presented instead of ordinary means (SD). A log transformation will be applied to achieve normality and if not achieved, alternative tests such as the Wilcoxon rank sum test will be used to compare outcomes between trial arms. If normality is achieved through log transformation, then the parametric tests described in sections 5.2.1, 5.2.2 and 5.2.3 will be applied to the log transformed data and results back-transformed to be presented as geometric mean ratios (GMR) and 95% CIs. The assumption of equal variances will be checked by testing if standard deviations of the two sample outcome responses are approximately equal e.g., using the F test. If the variances are found to differ, a t test allowing for unequal variance will be used.

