# Shell table shows weeks -8 and 0 only for reasons of space in this document; additional columns in the same format as that shown for weeks -8 and 0 will be included for weeks 4, 8 and 52.

\*P values reported from chi square test

\*\* Estimate and P value from GEE

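### Malaria intensity has three incompatible analyses in the SAP, and Table 6 as drawn compares it only among participants still infected

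*SAP*

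**What the plan says.** Four parts of the SAP describe the malaria outcomes.

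- **Definition (5.1.2):** "Infection status (infected and uninfected) and intensity (light, medium and heavy". No cut-points or units are given, and the intensity classes do not include uninfected.
- **Analysis (5.2.2):** at each visit, "the means (SD) of malaria infection intensity will be presented by trial arm, and comparisons between trial arms will be made using unpaired t-tests". It then adds "For both malaria infection status and intensity, Generalised Estimating Equations (GEE) will be used" without naming a distribution, link or working correlation.
- **Reporting (5.5.3, Table 6):** the intensity block has the rows Light, Medium and Heavy, as n (column %). The footnote to the P value columns reads "P values reported from chi square test".
- **Non-normal data (Checking assumptions):** "A log transformation will be applied to achieve normality and if not achieved, alternative tests such as the Wilcoxon rank sum test will be used".

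The visits also differ. Section 2.7 lists "Current malaria infection status and intensity at screening (week -8), weeks 0, 4, 8, 52", and Table 6 uses the same weeks. Section 3.3 lists results "on immunisation days (weeks 0, 4, 8 and 28", together with baseline at week -8 and the endpoint days.

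Section 4.2 counts malaria infection status among the baseline characteristics and states "No statistical tests will be done to compare baseline characteristics between arms". Table 6 nevertheless has a P value column at week -8.

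**The concern.** An outcome with three ordered classes has no mean unless scores are assigned, and a chi-square P value is not a t-test P value. An analyst cannot follow 5.1.2, 5.2.2 and Table 6 together, so the choice would be made at analysis, possibly with results in view.

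The more consequential gap is the uninfected participant. Nothing says how such a person is scored on intensity. In Table 6 they have no row in the intensity block, so a test of that block uses only people still infected at that visit. Once treatment has started, being infected is itself an outcome of treatment, and the two infected groups are no longer comparable by randomisation.

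The numeric route has the same gap. If intensity is a parasite density, the log step in the assumption checks is undefined at zero, and uninfected participants drop out unless a rule is given. None is.

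At stake is the intensity half of secondary objective (d), effects on malaria prevalence and intensity.

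**Working it through.** **1. The passages side by side**

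| Place in SAP | Scale | Test | Uninfected | Weeks |
|---|---|---|---|---|
| 5.1.2 | light, medium, heavy | none named | not in the intensity classes | refers to 2.7 |
| 5.2.2 | mean (SD) | t test, plus GEE of unstated form | not stated | each timepoint |
| Table 6 | counts in three classes | chi-square, plus GEE | no row in the intensity block | -8, 0, 4, 8, 52 |
| 3.3 | not stated | not stated | all enrolled with results | -8, 0, 4, 8, 28, 52 |

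Scale and test conflict between the first three rows. Week 28 appears only in 3.3. Space does not explain its absence from Table 6, because the note under the table names the extra columns as weeks 4, 8 and 52. Section 3.3 also counts week 8 as an immunisation day, while the opening of 2.7 places immunisations at weeks 0, 4 and 28. These passages must be reconciled.

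**2. Size of the infected-only problem (illustration)**

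The SAP gives no figure for intensity, so there is none to reproduce. Its power table concerns vaccine responses.

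- From section 2.2: 341 randomised and 20% loss; from section 2.1: 1:1 allocation. 341 / 2 × 0.8 = 136 per arm.
- Assumed: placebo none/light/medium/heavy = 40/30/20/10%.
- Assumed: scores of 1, 2, 3 for the classes, and 0 for uninfected where they are included.

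Among the infected, the mean score is (1 × light + 2 × medium + 3 × heavy) / (light + medium + heavy). Over all participants it is the numerator alone.

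Placebo numerator: 0.30 + 0.40 + 0.30 = 1.00. Infected-only mean: 1.00 / 0.60 = 1.67. Infected: 136 × 0.60 = 82.

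*Scenario A, DP clears 70% of every class: DP = 82/9/6/3%.*
- Infected on DP: 136 × 0.18 = 24, with classes 50/33/17%, the same as placebo.
- Infected-only three-class chi-square: no difference to detect, so power equals the 5% level.
- Four-class chi-square with uninfected included: noncentrality 68 × (0.42²/0.61 + 0.21²/0.195 + 0.14²/0.13 + 0.07²/0.065) = 50.4 on 3 df, power about 100%.

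*Scenario B, DP clears 90% of light infections only: DP = 67/3/20/10%.*
- Numerator: 0.03 + 0.40 + 0.30 = 0.73. Infected-only mean: 0.73 / 0.33 = 2.21.
- Infected-only difference: 2.21 - 1.67 = +0.55 (unrounded 0.545), so DP looks worse.
- All participants: 0.73 - 1.00 = -0.27, so DP is better.

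*Scenario C, mostly medium and heavy infections cleared: DP = 70/25/4/1%.*
- Numerator: 0.25 + 0.08 + 0.03 = 0.36. Infected-only mean: 0.36 / 0.30 = 1.20.
- Infected-only difference: 1.20 - 1.67 = -0.47. All participants: 0.36 - 1.00 = -0.64. The direction agrees.

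**3. How few people the infected-only test may use**

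Again on assumed prevalences: 10% infected on DP and 50% on placebo gives 136 × 0.10 = 14 versus 136 × 0.50 = 68. With 5% and 40% it is 7 versus 54. Then 90% to 95% of the DP arm does not enter the intensity test.

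**The case against.** A reader might infer that the intensity analysis is selection-biased as planned. The text does not support that. No sentence restricts the analysis to infected participants. Section 3.3 takes all enrolled participants with samples and results, and the t test in 5.2.2 could include the uninfected as zero. The problem arises if the Table 6 block is tested as drawn, or if uninfected participants are lost at the log step. This objection stands, and the point is therefore conditional. It does not remove the gap, because 3.3 covers status and intensity together and never says how an uninfected person is scored.

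A reader might also infer that the trial could not show whether DP cleared infection. That does not follow. The Positive/Negative rows of Table 6, the per-visit comparison of proportions and the GEE on status would show clearance whatever happens to the intensity rows.

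On week 28, it is tempting to say that data exist and are being dropped. The SAP does not establish that malaria was measured then, and the list in 3.3 is itself at odds with 2.7 on week 8. Nor does a missing visit cause selection on infection.

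Finally, 5.1.2 need not be the intended scale. Means, a log transformation and a rank-sum fallback suggest that a numeric density may be meant, so an ordinal model is one sound option among several. Chi-square ignoring the order of the classes costs efficiency but is not an error.

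**Conclusion.** The inconsistency is established from the text alone: one secondary outcome has three descriptions of scale and test that cannot all be followed, no scoring rule for uninfected participants, two visit lists, and a week -8 P value that contradicts section 4.2.

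The threat to inference is conditional. If Table 6 is analysed as drawn, its intensity comparisons after treatment starts can miss an effect (5% power in scenario A) or reverse it (+0.55 against -0.27 in scenario B). Scenario C shows that it need not mislead. These figures rest on assumed class distributions and equal-step scores, because the SAP gives no intensity distribution. Week -8, which the SAP treats as screening and baseline, is not exposed to this problem.

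The infection-status comparison, the primary vaccine-response analyses and the power table are unaffected. The point should be corrected before the malaria data are analysed by arm, but it does not endanger the trial's main result.

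**What to change.** 1. Choose one scale and score every participant with a result on it. Either:
   - ordered none/light/medium/heavy, with cut-points stated, and an ordinal or rank-based test; or
   - parasite density with units, uninfected scored as zero, and a method that allows zeros.
2. Match the per-visit test in 5.2.2, the GEE (distribution and link stated) and the Table 6 footnotes to that scale.
3. Add an uninfected row to the intensity block of Table 6. If intensity among the infected is also of interest, label it descriptive.
4. Give the same visit list in 2.7, 3.3 and Table 6, and report week 28 if malaria was measured then.
5. Remove the week -8 P value from Table 6 to agree with 4.2.

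The cost is SAP wording and a revised table shell. Nothing here requires new data collection.

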### Checking assumptions

For statistical analyses that require data to be normally distributed, the normality assumption of the data will be checked using graphical assessment of normality (Q-Q plot) and a Kolmogorov-Smirnov test for normality. If the data are found to be non-normal, medians (IQR) or geometric means (SD) will be presented instead of ordinary means (SD). A log transformation will be applied to achieve normality and if not achieved, alternative tests such as the Wilcoxon rank sum test will be used to compare outcomes between trial arms. If normality is achieved through log transformation, then the parametric tests described in sections 5.2.1, 5.2.2 and 5.2.3 will be applied to the log transformed data and results back-transformed to be presented as geometric mean ratios (GMR) and 95% CIs. The assumption of equal variances will be checked by testing if standard deviations of the two sample outcome responses are approximately equal e.g., using the F test. If the variances are found to differ, a t test allowing for unequal variance will be used.

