# 2. Study Methods

# 2.1. Trial design

This trial is a randomised, double-blind, placebo-controlled, parallel group trial comparing effect of monthly preventive treatment of malaria with dihyrodartemisinin-piperaquine (DP) versus placebo on vaccine response outcomes. Treatment allocation is a 1:1 ratio for the trial intervention.

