#### 2.2. Sample size considerations

The original target sample size was 640 healthy adolescents (320 in each arm) of whom 60% (384) were expected to have malaria infection at the outset will be enrolled into the trial. This target sample size was informed by the expected difference in vaccine responses between the two arms, with full details of sample size considerations presented in the protocol. However, due to the onset of the COVID-19 pandemic and the consequent restrictions in Uganda, it was not possible to achieve the original target sample size. Table 1 shows updated power estimation for the achieved sample size of 341.

Table 1. Updated power estimates for the primary analysis population of participants with
malaria infection at baseline (5% significance level): n=341, assuming 60% malaria
neoral and allowing for 200/ less to follow up

	Log 10 difference						
Standard deviation (log 10 )	0.10	0.12	0.14	0.16	0.18	0.20	
102 DP vs 102 placebo (baseline malaria infected only), 20% loss to follow-up, i.e. analysis based on 82 vs 82							
0.3	56%	72%	84%	92%	97%	99%	
0.4	36%	48%	61%	72%	82%	89%	
0.5	25%	33%	43%	53%	63%	72%	
0.6	19%	25%	32%	40%	48%	56%	
Cells highlighted in arey correspond to >80% nower							

prevalence, and allowing for 20% loss to follow-up

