# 3. Statistical Principles

# 3.1. Level of statistical significance

All applicable statistical tests will be 2-sided. All tests will be performed using a 5% significance level. 95% confidence intervals will be presented.

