### 5.5.2. Comparison of primary outcome responses between trial arms

Table 3: Differences in responses between DP and Placebo arms at week 8 for BCG, YF-17D, Ty21a, HPV and week 52 for Td.

	DP	Placebo			
Vaccine	Mean (SD)**	Mean (SD)**	Mean difference***	95% CI	P value*
BCG					
YF-17D					
Ty21a					
HPV					
Td					

\*P values reported from unpaired t test

\*\* If data are not normally distributed, median (IQR) or geometric mean (SD) will be presented

\*\*\* If data not normally distributed, Geometric Mean Ratios (GMR) will be presented

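### Normality checks on the trial data choose the scale and test for each primary vaccine response, so the estimand is not fixed and an outcome sent to a rank test has no defined effect estimate

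*SAP*

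**What the plan says.** Section 2.2 gives "Updated power estimates for the primary analysis population of participants with" malaria infection at baseline. Both margins of Table 1, the difference and the SD, are in log10 units. Section 1.2 states the null hypothesis in terms of mean responses. Section 5.2.1 names unpaired t tests and a mean difference with 95% CI, without naming a scale. It adds a possible adjustment for the baseline measure and an interaction with sex.

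The section on checking assumptions then sets a sequence. Normality is judged by a Q-Q plot and a KS test. If it fails, logs are taken: "A log transformation will be applied to achieve normality and if not achieved, alternative tests such as the Wilcoxon rank sum test" is the next step. A GMR with 95% CI is promised only where the log transformation has achieved normality. A variance check, with the F test as an example, picks the form of the t test: "If the variances are found to differ, a t test allowing for unequal variance will be used".

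The footnote to Table 3 (section 5.5.2) is broader: "If data not normally distributed, Geometric Mean Ratios (GMR) will be presented". The same shell attributes every p value to the unpaired t test.

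**The concern.** The scale is known well enough in advance to plan power on it, yet the analysis leaves it open until the data are in. No threshold is given. Nothing says what happens if plot and test disagree, or whether the check is done per arm or on pooled residuals. The fallback is itself open, because the rank test is named only as an example.

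The three branches estimate different things: a difference in arithmetic means, a ratio of geometric means, or a shift in ranks. Table 3 could therefore hold a mean difference for one vaccine, a GMR for another and a bare p value for a third. In the rank branch arm medians can be shown, but no between-arm effect measure or interval is defined. The baseline adjustment and sex interaction of section 5.2.1 have no stated form there either. That does not fit a hypothesis about means, the 95% CIs promised in section 3.1, or the Table 3 footnote.

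**Working it through.** **Inputs from the SAP.** 341 randomised, 1:1, 60% infected, 20% loss (section 2.2); two-sided 5% tests (section 3.1). Per arm: 341 × 0.60 / 2 = 102.3, and 102.3 × 0.80 = 81.8, which gives the stated 102 and 82.

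**Table 1 reproduced.** For a t test on log10 means the noncentrality is difference / (SD × √(2/82)), with 162 degrees of freedom and √(2/82) = 0.1562.

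| log10 SD | log10 difference | Noncentrality | Computed power | Table 1 |
|---|---|---|---|---|
| 0.3 | 0.14 | 0.14 / 0.0469 = 2.99 | 84.4% | 84% |
| 0.4 | 0.18 | 0.18 / 0.0625 = 2.88 | 81.7% | 82% |
| 0.5 | 0.20 | 0.20 / 0.0781 = 2.56 | 72.1% | 72% |
| 0.6 | 0.20 | 0.20 / 0.0937 = 2.13 | 56.4% | 56% |

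All 24 cells reproduce to within 1 point. The planned effects are already GMRs: 10^0.10 = 1.26 to 10^0.20 = 1.58.

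**When would an outcome reach the rank branch?** The following was simulated with 82 per arm and 2,000 trials per setting. The KS test was applied to pooled within-arm residuals, either with plug-in mean and SD or in the Lilliefors form. The SAP does not say which form it means and gives no assay distributions, so every non-log-normal case is an assumption. Entries show how often normality of the logs is rejected.

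| Data | Plug-in KS | Lilliefors |
|---|---|---|
| Exactly log-normal | about 0% | 3% to 5% |
| 10% of controls at a detection limit | 0% | 11% to 12% |
| 20% of controls at a detection limit | 6% to 15% | 74% to 88% |
| Two-fold titres, SD 0.6 to 0.3 | 34% to 96% | 93% to 100% |
| Four-fold titres, SD 0.6 to 0.3 | 97% to 100% | 100% |

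When plug-in KS is applied to each arm and rejection in either arm counts, two-fold titres are rejected in about 39% (SD 0.6) to 100% (SD 0.3) of trials.

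The cause is discreteness. A two-fold step is log10 2 = 0.301, about one SD when the SD is 0.3. One titre level centred on the mean then holds Φ(0.5) − Φ(−0.5) = 0.38 of an arm. A jump of that size forces a KS distance of at least 0.38 / 2 = 0.19, above the 5% critical value of about 1.358 / √82 = 0.150. The log analysis is not invalidated: an unequal-variance t test on these logs has about 5% type I error.

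**Does the rule cost power?** With log-normal data, following the SAP sequence gives 84.1% against 84.2% for always using logs (SD 0.3, difference 0.14), and 72.0% against 72.0% (SD 0.5, difference 0.20). Where Wilcoxon is used, its power stays within about 3 points of the unequal-variance t test:

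| Data | SD, difference | Unequal-variance t on logs | Wilcoxon |
|---|---|---|---|
| Log-normal | 0.3, 0.14 | 86.2% | 83.5% |
| Log-normal | 0.6, 0.20 | 57.9% | 54.9% |
| Two-fold titres | 0.3, 0.14 | 80.7% | 79.5% |
| Two-fold titres | 0.6, 0.20 | 56.2% | 54.6% |

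**F test.** On log-normal data after the log step it rejects in about 5% of trials, and its only effect is to switch to the unequal-variance t test.

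**The case against.** The sequence is written down in advance and ordered, and section 2.4 keeps the trial blinded until the data are analysed. Nothing here shows an inflated type I error, or suggests that the branch would be chosen to favour a result. The Q-Q plot gives the analyst room to stay on logs when KS rejects only because of discrete readings, whereas the simulated gate was KS alone. Of the five vaccines only yellow fever is described as a titre, so the dilution-step figures do not carry over to the others. The Table 3 footnote may be no more than shorthand for the text rule. All of this stands. It limits how often the problem would bite, but it does not supply an effect estimate for the rank branch, and reliance on judgement makes the branch less predictable.

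A reader might go further and infer that the stated power is not delivered, because a raw-scale t test on log-normal data has 76% power where Table 1 says 84% (SD 0.3, difference 0.14), and 48% where it says 72% (SD 0.5, difference 0.20). The SAP does not support that reading, since its rule moves such data to logs. Raw log-normal data passed plug-in KS in both arms in about 8% of trials at SD 0.3 and almost never at larger SDs. A reader might also cite the F test's 41% to 66% rejection rate for identical log-normal arms. That rate belongs to raw data which the rule would already have logged.

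**Conclusion.** The point holds as one about the estimand. The SAP lets the data choose between three effect measures for each primary outcome and defines none for the rank branch, while its hypothesis, its promised CIs and its Table 3 footnote all presume one. There is no material power loss and no demonstrated error inflation, and the F test matters little on logs. How likely the rank branch is depends on assay features that the SAP does not give. It is rare for exactly log-normal data, and likely for titres read in two-fold steps (about 39% to 100% under the per-arm KS gate). The change should be made, because it gives every primary outcome an interpretable estimate on the scale used for planning.

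**What to change.** State in section 5.2.1 that all primary vaccine responses are analysed on log10, with a fixed rule for zeros and values below detection. Use an unequal-variance t test, or the equivalent regression when adjusting for baseline or fitting the sex interaction, and report a GMR with 95% CI in every case. Remove the KS and F tests as gates. Keep Q-Q plots as description and the Wilcoxon test as a sensitivity analysis. Align the Table 3 footnotes, and correct the reference to section 5.2.3, which this SAP does not contain.

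The cost is SAP wording. Simulated power of the unequal-variance test on log-normal data is 86%, 82% and 58%, where Table 1 has 84% (SD 0.3, difference 0.14), 82% (SD 0.4, difference 0.18) and 56% (SD 0.6, difference 0.20). Any loss against the pooled t test is therefore negligible, and no sample size figure changes.
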